6.4.3.2 Economic Analyses

We will examine the total costs incurred by the NHS of providing care for patients with viral meningitis. The EQ-5D as mentioned before will be used for expressing the health outcomes as cost per Quality Adjusted Life Years (QALY). The cost analysis will follow the ingredients approach; costs and benefits will be discounted at 3.5%. Quantities will be reported separately from prices. Patients and carers will be asked to answer a socio-economic questionnaire to assess the costs incurred by them (non-medical direct costs, indirect costs, and accompany person costs).

Both of these analyses (SF36 and EQ5D) will be led by [name] [name], Senior Health Economist.

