1 PROTOCOL SUMMARY

Title: UK Meningitis Study: Epidemiology and outcomes in meningitis in the UK – A prospective, observational, cohort study.

Population: A study looking at adults admitted to hospitals in the UK with suspected meningitis.

Inclusion Criteria

- a. 16 years or over
- b. Suspected Meningitis AND either
 - i) Have had or are going to have a lumbar puncture
OR
 - ii) If Lumbar puncture is contraindicated: the clinician has a strong suspicion of meningitis AND positive blood culture for bacterial pathogen consistent with meningitis OR radiology consistent with meningitis AND being treated as meningitis.

Exclusion Criteria

1. Patients with indwelling ventricular devices (EVD, VP shunts etc...) or iatrogenic meningitis
2. Patients in whom a lumbar puncture is contraindicated (except see b(ii) above)

Number of Sites: 35-45

Study Duration: 2 years extended to 5 years

Objectives:

[figure not shown]
Primary:

- To determine the prevalence of viral meningitis in adults hospitalised with suspected meningitis and how much of viral meningitis is attributable to herpes viruses, and other viruses.

Secondary:

- To examine the clinical and laboratory features, time to symptom resolution, neurological complications, neuropsychological sequelae, and recurrences in viral meningitis
- To compare these features and outcomes with those in bacterial meningitis and non-meningitic controls
- To prospectively evaluate the *Meningitest* – an algorithm for predicting viral or bacterial aetiology in meningitis
- To determine the number of people with aseptic meningitis being offered an HIV test and the proportion of these that are positive.
- To determine and describe the causes of aseptic meningitis in our region.
- To determine the costs to the NHS and to the patients.
- To determine the impact on the patient's quality of life.
- To evaluate the use of certain outcome measures in viral meningitis (HIT, ABNAS).
- To use these epidemiological and disease burden data to design a phase III study of aciclovir / valaciclovir in herpes meningitis.
- To evaluate new genomic and proteomic approaches in the diagnosis of meningitis.
- To evaluate new diagnostic techniques and methods
- To identify themes and barriers amongst clinicians and laboratory staff that may be associated with implementing new diagnostic tests for meningitis.

Schematic of Study Design

1.1 Substantial Amendment 17

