2.2 Potential Risks and Benefits

2.2.1 Potential Risks

Risks include loss of confidentiality. Good Clinical Practice should ensure this does not happen. Physical risks are limited to those of the extra venepuncture including bruising. The extra blood tests will, where possible be done at the same time as routine venepuncture to minimise this risk. There are no other potential physical risks to the participants as this is an observational study. The clinical care is directed by the responsible physician. There may be psychological risks as participants recall the impact their illness has had on their quality of life.

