6.4.5 Amendment 09 (17/09/2012)

Early analysis has shown that there is no difference between the control patients and the viral meningitis patients (n=20 in each group). Therefore, it is postulated that as our control patients are patients that have been hospitalised a more 'healthy' control group is needed. Therefore, we will ask the participants when they are filling in the questionnaires to also give a pack of questionnaires to a relative/friend/neighbour to also fill in and return. Data on age and gender will be collected on these healthy controls.

The HIT, SF-36, ABNAS, and EQ-5D will be performed at 6, 12, 24 and 48 weeks after discharge. Each of these is a patient self-completed questionnaire which collectively will take twenty to thirty minutes to complete. It is important to obtain these serial evaluations so that we can determine the best endpoint for the subsequent treatment study.

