9 ETHICAL CONSIDERATIONS

9.1 Ethical Considerations

The study will abide by the principles of the World Medical Association Declaration of Helsinki (1964) and Tokyo (1975), Venice (1983), Hong Kong (1989) and South Africa (1996).

Ethical problems to be encountered in this study would include;

- Consenting of acutely ill patients. This problem can be countered by the fact that patients will be able to be recruited at any point during their acute admission and this can be either before or after the lumbar puncture +/- any treatment.
- We will be requesting extra blood and CSF samples for our genomics and proteomics work as well as storage for other future studies. This may provide anxiety to the patient who will be allayed by the patient information leaflet and reassurance that the sample will be pseudonymised and the samples will only be used for indications that they have consented to. Samples will be stored securely at the University of Liverpool.
- The use of questionnaires means that some data will have to be pseudonymised, as we will still need to access the participant's name and address. Reassurance will be given to the participant regarding confidentiality and no medical information will be divulged on the questionnaires. The completed questionnaire on return will have no identifying features.
- The study can include someone who lacks capacity (see section 9.1.1). Advice will be taken from a consultee (carer/family member) in accordance with GCP and the Mental Capacity Act (2005).
 - **Substantial Amendment 15 (August 2015) – no patient who lacks capacity will be recruited in sites in Scotland.**
- It is possible that participants may consider that they will get better/different treatment by either being in or not being in the study. All patients will be treated by their responsible physician and any treatment will not be influenced by the study. It will be emphasised that the study is observational and not interventional.

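### Protocol 6.4.3.2 plans a cost per QALY, but the study compares no alternative care strategies economically, so the ratio cannot be interpreted; costs and QALYs should be reported separately.

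*Protocol*

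**What the plan says.** Section 6.4.3.2 opens with the costing: "We will examine the total costs incurred by the NHS of providing care for patients with viral meningitis". It goes on: "The EQ-5D as mentioned before will be used for expressing the health outcomes as cost per Quality Adjusted Life Years (QALY"). It also specifies an ingredients approach, a 3.5% discount rate, quantities reported apart from prices, and a questionnaire on costs borne by patients and carers.

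The economic objective in the Protocol Summary concerns cost alone: "To determine the costs to the NHS and to the patients". Section 7.1.2 lists the economic analyses with EQ-5D as secondary outcome (g) and names no comparison.

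On design, the title describes "A prospective, observational, cohort study". Section 2.2.1 says "The clinical care is directed by the responsible physician", and section 9.1 says "It will be emphasised that the study is observational and not interventional".

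On timing, section 6.4.5 says "The HIT, SF-36, ABNAS, and EQ-5D will be performed at 6, 12, 24 and 48 weeks after discharge", and the schedule in 6.7 agrees. Comparison groups exist for outcomes: bacterial meningitis and non-meningitic controls (Protocol Summary and 5.1), and from Amendment 09 a relative, friend or neighbour of the participant, for whom age and gender are collected (6.4.5).

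**The concern.** Cost per QALY answers one question: what is paid for each unit of health gained when one course of action replaces another. It needs two courses of action, with costs and QALYs for both. Section 6.4.3.2 names one patient group and one set of NHS costs, and it describes the ratio as a way of expressing health outcomes, which a ratio with cost in the numerator cannot do.

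This is a matter of what the protocol states, not of detail left for later: the summary measure is named, and it does not fit the design. The study is meant to supply burden data for a treatment trial (2.1). That trial's designers will need cost per case and health loss per case, each with its uncertainty. A single ratio hides both, and a reader may compare it with cost-effectiveness results it does not resemble.

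**Working it through.** The protocol gives no cost, utility or cost-per-QALY value, so there is no figure to reproduce. The check takes each reading of the sentence in turn.

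**Inputs.** NHS cost C for viral meningitis patients only (6.4.3.2); EQ-5D at 6, 12, 24 and 48 weeks after discharge (6.4.5, 6.7); a further questionnaire at 2 years for some patients, contents not stated (6.4.6); comparison groups defined by diagnosis or by being healthy (5.1, 6.4.5).

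**Reading 1: cost divided by QALYs lived.** With mean utility u over a horizon of H years, ratio = C / (u × H).

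- At 48 weeks, H = 48/52 = 0.923.
- If only the measured period counts, H = (48 − 6)/52 = 42/52 = 0.808. With C and u unchanged, the ratio is 48/42 = 1.14 times the 48-week value.
- At 2 years, assuming the same u, no added cost and no discounting, the ratio is 0.923/2 = 0.46 of the 48-week value.

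None of these changes reflects the illness or its care; only the horizon has moved. The two parts also cover different periods: total NHS cost includes the admission, while the first EQ-5D is 6 weeks after discharge.

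**Reading 2: difference from a control group.** Ratio = (C₁ − C₀) / (Q₁ − Q₀), where 1 denotes cases and 0 controls.

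- If cases cost more and have fewer QALYs, the numerator is positive, the denominator negative and the ratio negative.
- A group that cost less and had more QALYs would also give a negative ratio, so the sign does not separate opposite situations.
- Multiplying both differences by the same factor k leaves the ratio unchanged: kΔC / kΔQ = ΔC / ΔQ. It cannot show how large the burden is.
- C₀ is not provided for. The NHS costing in 6.4.3.2 covers viral meningitis, and 6.4.5 describes questionnaires, age and gender for the healthy controls, with no NHS costing.

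More basically, having bacterial meningitis, having no meningitis and being a healthy neighbour are not options a payer chooses between.

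**Reading 3: a contrast of treatments within the cohort.** Section 2.1 notes that some physicians give aciclovir and others do not. No section plans an economic comparison of the two.

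**What the data do support.** With linear interpolation between visits, QALYs over the measured period are

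[6(u₆ + u₁₂)/2 + 12(u₁₂ + u₂₄)/2 + 24(u₂₄ + u₄₈)/2] / 52 = (3u₆ + 9u₁₂ + 18u₂₄ + 12u₄₈) / 52.

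The weights sum to 42, so full health throughout gives 42/52 = 0.808. This quantity can be calculated in cases and in any control group completing EQ-5D at the same visits, and the two can be subtracted without a ratio.

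**The case against.** The strongest reply is that this is one loosely worded sentence. The cost objective is already served: 6.4.3.2 plans total NHS costs, an ingredients approach, quantities kept apart from prices, and patient and carer costs. A senior health economist leads the work, and horizon and comparator are details commonly left to an analysis plan, which is not at hand here. All of that stands, and the missing detail is not criticised. What remains is that the named measure presupposes a comparison the design does not contain, and a later plan could only replace it.

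It is also fair to say that the study has comparators. It does, for clinical outcomes and quality of life, and they can support an estimate of QALY difference. They do not supply an alternative use of resources.

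Two stronger readings are tempting, and the documents support neither.

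- A reader might infer that the ratio would make worse disease look cheaper. That depends on a case-minus-control formula the protocol never defines and on cost staying fixed as harm grows. Cost over QALYs lived goes up, not down, as utility falls at fixed cost, and under other formulas the direction can change once cost also rises.
- A reader might infer that discounting is an error because EQ-5D ends at 48 weeks. The section says only that "costs and benefits will be discounted at 3.5"%; it does not say the rate applies within the first year, and the 2-year questionnaire leaves later data possible.

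**Conclusion.** The point holds in a limited form. As worded, 6.4.3.2 commits the study to a ratio that is neither a cost-effectiveness result nor a measure of burden, because no alternative care strategies are compared economically. This follows from the protocol's description of the design and the costing, not from any assumed cost or utility. The horizon factors (1.14 and 0.46) assume constant utility and no added cost, and the negative sign against controls assumes that cases cost more and have fewer QALYs.

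The effect is confined to secondary outcome (g). The primary prevalence outcome, the sample size, the clinical comparisons and the cost objective are untouched. A reader might infer that the whole economic analysis fails; it does not. The costing can proceed as planned, and the EQ-5D data are usable once taken out of the ratio.

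**What to change.** In 6.4.3.2, delete the cost-per-QALY sentence and state two separate results, each with a confidence interval:

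1. NHS cost and patient/carer cost per viral meningitis case, as the section already plans.
2. EQ-5D utilities at each visit and QALYs over 6 to 48 weeks after discharge, or the QALY difference from a named control group, adjusted for age and gender.

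Add that cost per QALY is left to the later treatment trial.

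This changes wording only and needs no new data. The downsides are small. There will be no single summary ratio. The period before week 6 has no EQ-5D measurement, so a QALY figure that includes the acute illness must be labelled as resting on an assumption. The healthy controls are a convenience group chosen by participants, with only age and gender available for adjustment, and the report should say so beside any difference from them.

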There is currently no consensus for the treatment of herpes virus meningitis. In particular there has not been a Cochrane review, hence the need for a study to assess this. Some clinicians treat patients with intravenous aciclovir (or its oral pro-drug valaciclovir), because studies have shown it is effective in encephalitis caused by HSV (10, 11). Indeed in some centres all patients with aseptic meningitis are treated this way, whether or not HSV infection is proven. In contrast other physicians discharge patients without treatment, because there is no evidence for efficacy, and the drug has rare but important side effects, such as renal failure. The use of aciclovir in the treatment of herpes virus meningitis has been identified by experts in the field as a key question that needs addressing by a randomised study (2, 12).

This current study is planned as a preliminary study to produce outcome data needed for the design of such a study.

- Need for improved diagnostics

As aseptic meningitis often results in no pathogen identified it may prevent patients receiving prompt appropriate medical management and may lead to poor utilisation of drugs, i.e. antibiotics and aciclovir. Further work by our group is planned with respect to evaluating newer genomic and proteomic approaches to diagnosis. This is outlined in section 6.8.3

Objectives

- 1) To determine the prevalence of viral meningitis in adults and how much is attributable to herpes viruses, and other viruses.
- 2) To examine the clinical and laboratory features, time to symptom resolution, neurological complications, neuropsychological sequelae, and recurrences in viral and bacterial meningitis, and non-meningitis controls.
- 3) To prospectively evaluate the *Meningitest* – an algorithm for predicting viral or bacterial aetiology in meningitis
- 4) To determine the number of people with aseptic meningitis being offered an HIV test and the proportion of these that are positive.
- 5) To determine and describe the causes of aseptic meningitis in our region.
- 6) To determine the costs to the NHS and to the patients.
- 7) To determine the impact on the patient's quality of life.
- 8) To evaluate the use of certain outcome measures in viral meningitis (HIT, ABNAS).
- 9) To use these epidemiological and disease burden data to design a phase III study of aciclovir / valaciclovir in herpes meningitis.

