7.1.2 Secondary

- a. Time to fever resolution
- b. Resolution of acute morbidity (using the TMS)
- c. Incidence of relapse and recurrence
- d. Change in Headache Impact Test over the study period
- e. Quality of Life Assessment (SF36)
- f. Neuropsychological Outcome (ABNAS)
- g. Economic Analyses (EQ5D)
- h. To determine the number of people with aseptic meningitis being offered an HIV test and the proportion of these that are positive.
- i. Pathogen Specific Outcomes
- j. Clinical Predictors of outcome or pathogen.

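### Cost per QALY is named as the economic expression in a cohort with no intervention or comparator, so the ratio's meaning, sign and direction are undetermined

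*Protocol*

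**What the plan says.** Section 6.4.3.2 of the protocol opens with the cost side: "We will examine the total costs incurred by the NHS of providing care for patients with viral meningitis". It then says that EQ-5D "will be used for expressing the health outcomes as cost per Quality Adjusted Life Years (QALY"). It names no alternative course of care, no comparator group, and no difference in cost or in QALYs.

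Section 9.1 describes the design: "It will be emphasised that the study is observational and not interventional". It adds that "any treatment will not be influenced by the study".

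The economic objective in section 2.1 (number 6) is "To determine the costs to the NHS and to the patients". Objective 7 is the effect on quality of life. No objective concerns cost-effectiveness. Section 7.1.2 lists the outcome as item (g), "Economic Analyses (EQ5D"), without a contrast.

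Section 6.4.5 schedules EQ-5D at weeks 6, 12, 24 and 48 from discharge. It also adds healthy controls (a relative, friend or neighbour), who complete the questionnaires and give age and gender. No cost data are described for them.

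**The concern.** A cost per QALY has a decision meaning when one course of action is set against another: the extra cost divided by the QALYs gained. Here the groups differ by diagnosis and nobody chooses between them. The health outcome that EQ-5D can supply is a utility or a QALY total, and section 6.4.3.2 instead expresses that outcome as a ratio with cost in it.

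Because no contrast is fixed, at least three quantities fit the wording, and they behave differently. An analyst could compute any of them and label it cost per QALY. The reader of secondary outcome (g) would then hold a figure that looks like a value-for-money result and is not one. It would also tell them neither what viral meningitis costs nor how much quality-adjusted life it takes away.

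**Working it through.** The protocol gives no cost, no QALY total and no ratio, so there is no figure to reproduce. The check is whether any reading of the sentence gives an interpretable quantity.

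**Inputs from the protocol.** Last EQ-5D assessment at 48 weeks (section 6.4.5). No intervention (section 9.1). Cost described only as the total to the NHS (section 6.4.3.2).

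**Assumptions, not in the protocol.** Cost, or excess cost, C = 3,000 pounds per patient; reference utility 0.90; constant utility loss L between 0 and 0.20; horizon T = 48/52 = 0.923 year.

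**Formulas.**
- (A) Incremental against controls: C / (-L × T)
- (B) Per QALY lost: C / (L × T)
- (C) Total cost over QALYs lived: C / ((0.90 - L) × T)
- QALYs lost, as a separate quantity: L × T

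Worked example at L = 0.20: L × T = 0.185. (A) is 3,000 / -0.185 = -16,250. (B) is +16,250. (C) is 3,000 / (0.70 × 0.923) = 4,643. The table uses unrounded values.

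| Utility loss L | QALYs lost | (A) | (B) | (C) |
|---|---|---|---|---|
| 0 | 0 | undefined | undefined | 3,611 |
| 0.02 | 0.018 | -162,500 | 162,500 | 3,693 |
| 0.05 | 0.046 | -65,000 | 65,000 | 3,824 |
| 0.10 | 0.092 | -32,500 | 32,500 | 4,062 |
| 0.20 | 0.185 | -16,250 | 16,250 | 4,643 |

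With C at 1,000 or 5,000 the pattern is the same, since C only scales each ratio. A window counted from week 6 (42/52 year) multiplies all three ratios by 48/42 and also leaves the pattern unchanged.

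**What the readings show.** (A) is negative, and (A) and (B) both shrink in size as harm grows: ten times the loss gives one tenth of the ratio. (C) is positive, always defined, and rises with harm. But at L = 0 it is already 3,611, which is 78% (0.70 / 0.90) of its value at L = 0.20. It is mainly cost divided by background health.

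**How far the behaviour of (A) depends on assumptions.**
- Excess cost 3,000 + 20,000 × L: from -184,167 at L = 0.02 to -37,917 at L = 0.20. It still shrinks.
- Excess cost 300,000 × L²: from -6,500 to -65,000. The direction reverses.
- Controls cost 500 more than patients: from +27,083 to +2,708. The sign reverses.

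So sign and direction depend on choices and facts that the protocol does not fix. Only the separate quantity, QALYs lost, rises with harm from zero under every row of the table.

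**The case against.** The strongest reply is that this is loose wording about one secondary outcome. The comparator and horizon are commonly set in a later analysis or health-economics plan, and section 6.4.3.2 assigns the work to a senior health economist. Much of what a reader needs is already planned apart from the ratio: NHS costs by the ingredients method with quantities shown apart from prices, patient and carer costs by questionnaire, and SF-36 as its own secondary outcome (e). This stands, and it limits the severity. It does not remove the point, because the protocol names the metric, and a later plan that added a comparator would not create an intervention.

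Three stronger readings are tempting, and the documents do not support them.

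- A reader might infer that the ratio must be negative or undefined and must rank burden backwards. That holds only for an incremental ratio against controls who cost less and have more QALYs, with cost rising no faster than in proportion to the loss. Section 6.4.3.2 does not say the ratio is incremental. The hospital controls in section 5.1 include patients with other significant illness, so even the sign of the cost difference is open.
- A reader might infer from section 6.4.5 that the denominator will be near zero: "Early analysis has shown that there is no difference between the control patients and the viral meningitis patients (n=20 in each group"). That statement names no EQ-5D or QALY result, and the protocol responded by adding healthy controls. Amendment 17 (section 6.4.6) later mentions significant differences at 48 weeks, without naming the measure.
- A reader might infer that costs and quality of life go unmeasured, or that the ratio will mislead the phase III design. The components are collected, and although objective 9 uses the study's data for that design, no section says this ratio will be used.

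**Conclusion.** The point holds in limited form. Section 6.4.3.2 names cost per QALY as the expression of the health outcome in a study with no intervention and no defined comparator or increment. The ratio's numerator, denominator, sign and direction are undetermined. Against controls it may be negative, unstable, or smaller as QALY loss grows; as total cost over QALYs lived it mainly reflects background health. On none of the three readings is it a cost-effectiveness result or an answer to objectives 6 and 7.

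Severity is minor. Only secondary outcome (g) is affected; the primary outcome and the sample size are not. The conclusion about meaning rests on the protocol text alone. The pound figures rest on the assumed costs, reference utility and losses listed above, and show behaviour rather than expected size.

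**What to change.** In section 6.4.3.2, replace the cost-per-QALY sentence with text to this effect:

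- Report mean NHS cost and mean patient cost per case, each with a confidence interval.
- Separately, report EQ-5D QALYs over the observed follow-up (weeks 6 to 48 from discharge), with the difference from the hospital controls and from the healthy controls, adjusted for age and gender, each with a confidence interval.
- State that no cost/QALY ratio is calculated in this study, and that costs and utilities are kept as inputs for the economic model of the later treatment trial.

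The cost is a short replacement for one sentence. No extra data are needed: costs and EQ-5D are already collected from patients, and section 6.4.5 already provides for healthy controls' questionnaires with age and gender. The fix asks for no cost contrast with the healthy controls, for whom no cost data are described.
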